4.15.1 Safety Bloods

4.15.1.1 *TRIAL Participants*

SCREENING AND BASELINE

All blood tests detailed below will be required at screening and baseline. A serum beta HCG will only be required at baseline to exclude early pregnancy prior to initiation of GnRHa.

Baseline blood tests will usually require anyone on contraceptive treatment (and other hormones as indicated) to have a washout period – where the hormones are not taken – prior to the blood test to ensure true basal hormone panel blood results are interpreted accurately. This will be a clinical decision that takes account of risk of becoming pregnant (and will consider the potential to move to other forms of contraception). The length of washout period is dependent on the type of medication the CYP is using and there may be some circumstances where a washout period is not required. The baseline blood test may need repeating if the washout period needs to be extended to show gonadal axis function. The length of washout period is

to be discussed with and determined by the expert endocrine panel. This panel consists of experienced paediatric endocrinologists from the UK and EU.

Screening blood tests do not require a washout period. Blood tests are to be repeated at the baseline visit if more than 3 months has elapsed since screening.

FOLLOW UP VISITS

At 6-monthly follow-up visits, the following blood tests are mandated: FSH, LH, Oestradiol, Testosterone, Renal Profile, Full Blood Count, Magnesium, Prolactin, Lipid and Bone Profiles. Additional blood tests may be ordered by the PI or SI where clinically indicated. These may include tests outside the standard panel, based on individual participant needs or emerging safety concerns.

HAEMATOLOGY

FULL BLOOD COUNT:

Haemoglobin Platelet count Total and differential leukocyte count
(neutrophils, lymphocytes, monocytes, eosinophils, basophils.) Haematocrit
Red blood cell count

BIOCHEMISTRY

RENAL PROFILE:

Sodium Potassium Creatinine Urea

LIVER PROFILE:

Alanine Transaminase (ALT) Aspartate Aminotransferase (AST) Alkaline
Phosphatase (ALP) Bilirubin Albumin Total Protein

LIPID PROFILE:

Total Cholesterol HDL LDL

BONE PROFILE:

Calcium Phosphate Parathyroid Hormone (PTH)

OTHER:

Ferritin Follicle Stimulating Hormone (FSH) Luteinising Hormone (LH)
Oestradiol Testosterone Prolactin Thyroid Stimulating Hormone
Free T4 Vitamin D

4.15.1.2 HORIZON INTENSIVE Participants

HORIZON INTENSIVE participants will complete the same blood tests as TRIAL participants at baseline and month 24.

The electronic version of this document is the latest version. It is responsibility of the individual to ensure that any paper material is the current version. Printed material is uncontrolled documentation.

4.15.2 Pregnancy Tests

Pregnancy tests will only be conducted in TRIAL participants of child-bearing potential.

SERUM PREGNANCY TEST:

Serum beta-hCG will be determined for birth-registered female study participants of child-bearing potential prior to dosing. Serum testing is mandated at screening and baseline. Thereafter urine pregnancy testing is permitted but if not available, serum testing is acceptable.

URINE PREGNANCY TEST:

Urinary pregnancy testing will be required at screening and follow-up visits.

At baseline, if the delay waiting for serum pregnancy test results will make randomisation impossible, a urine beta-hCG pregnancy test may be used in addition to (not instead of) the serum pregnancy test to allow the site pharmacy adequate time post-randomisation to prepare the study medication for dispensing on the same day.

4.15.3 Urinalysis

Urinalysis will be performed at baseline and follow-up visits and is required for monitoring of potential rare side-effects of GnRHa. Part of the urinalysis is to monitor participants' glucose level as diabetes is a potential side effect of the medication.

Ketones	Urobilinogen
Bilirubin	Leukocyte esterases
Protein	Blood
Glucose	Nitrite

If urinalysis is positive for protein, blood, nitrite and/or leukocyte esterase, a microscopic examination (for red blood cells, white blood cells, bacteria, casts, and epithelial cells) will be performed.

4.16 Injection Visit Safety Data Collection

As per the schedule of events (table 2), if participants are switched to alternative IMPs with 3-monthly or monthly administration, a brief safety visit will be conducted at each study medication administration visit, including the following reviews as a minimum:

- Vital signs
- Adverse event reporting
- Concomitant medication review
- Pregnancy test (POCBP only)

The electronic version of this document is the latest version. It is responsibility of the individual to ensure that any paper material is the current version. Printed material is uncontrolled documentation.

4.17 Magnetic Resonance Imaging Data

Participants consenting to take part in PATHWAYS CONNECT will undergo structural and functional MRI imaging (sMRI/fMRI) at baseline, month 12 and month 24 as per the Schedule of Events. HORIZON INTENSIVE participants will be scanned at baseline and 24 months only. The final scanning window will be 6 weeks before/after the final treatment administration.

4.17.1 MRI Imaging Protocol

Prior to the scan, the radiographer will screen the participant for any contraindications for MRI scanning such as metallic implants or devices using an established institutional procedure. We will have a range of options to try to make the MRI experience as pleasant as possible. Depending on the availability of equipment and participant preferences this may include for example, a mock scanner (a non-operational MRI scanner) to familiarize the participant with the scanning procedure; an interactive virtual reality (VR) setting while scanning. The VR system allows participants to interact with visual content using their eyes using a pair of MR-conditional cameras in the scanner. The eye video recordings can also be used to estimate their gaze (what they are looking at on the screen) but will not be recorded. The VR system can also be used to present stimuli that can be used to identify the associated patterns of brain activity. This should improve the success rates of acquiring good-quality images. There may be instances where the VR system has unforeseen technical failures, in which case we will still conduct the scan.

Guidance will be given to participants on how they can contact the radiographer using a buzzer and microphone throughout the scan in case they need to stop the scan or communicate any other relevant information. All participants will have hearing protection applied prior to scanning in the form of mouldable silicon earplugs and cushioned headphones. The total MRI scanning will take no more than 90 minutes (including set-up and allowing for breaks), with approximately 40-60 minutes of scan time, however, we aim to complete the scan within shorter time frames if possible.

MRI sequences will include (1) structural/anatomical imaging including T1, T2 and T2* weighted images (2) diffusion-weighted imaging (uses the diffusion of water molecules to inform on tissue microstructure), (3) functional imaging (uses changes in blood oxygenation to inform on brain activity), (4) magnetic resonance spectroscopy (uses frequency information to inform on metabolite content, such as levels of NAA, Cr, Cho, glutamate, GABA, Glx & GSH), and (5) perfusion/susceptibility-weighted imaging (to inform on blood flow and content). Other acquisition sequences may be added if indicated, however the total time being scanned will not exceed 60 minutes. Any modified/customized acquisition sequences will adhere to the manufacturer's safety specifications and will be reviewed and authorized by the local MRI safety committee.

The electronic version of this document is the latest version. It is responsibility of the individual to ensure that any paper material is the current version. Printed material is uncontrolled documentation.

4.17.1.1 *Incidental Findings*

In the case of clinically significant incidental findings on MRI scan, the neuroradiology team will contact the participant's GP and the study team who will communicate with the family for further consultation/investigation if needed. Where it is deemed necessary, the participant's local Gender Service and paediatric team will also be informed. In this case, the report will be shared confidentially with designated individuals in the study team to facilitate communication with the family.

4.18 IMP Dosing Data

4.18.1 Study Medication Dispensing and Dosing Log

Study medication dispensing and dosing, including the IMP preparation being administered, or any active temporary or permanent discontinuation of study medication will be recorded on the study medication dispensing and dosing logs and stored in the site Pharmacy Files.

4.19 Measures to promote participant retention

To promote participant retention, the following measures will be implemented:

- Regular follow-up appointments with reminders sent via phone, email, or text message.
- Providing reimbursement for travel and expenses to participants and their parents/guardians
- Providing vouchers for completing outcome measures:
 - £30 for each cognitive assessment
 - £15 for each MRI scan.
 - HORIZON INTENSIVE participants will receive £15 for completion of DEXA scans and bloods
- Offering flexible scheduling for appointments to accommodate participants' availability.
- Ensuring a supportive and engaging environment during study visits.

5 Interventions

5.1 Explanation for the choice of comparators

The trial will compare immediate vs. delayed start (1 year) of GnRHa.

5.2 Intervention and comparator description, dosing and labelling and intervention

5.2.1 Medication:

The primary intervention all participants will initiate treatment on is Decapeptyl® SR (long-acting formulation of Triptorelin) 22.5mg intramuscular injection (6 monthly preparation).

5.2.2 Labelling:

The information presented on the IMP labels will be annex 13 compliant.

5.2.3 Administration:

The dose of Decapeptyl SR (long-acting formulation of Triptorelin) 22.5mg is administered every six months at 0, 6, 12, 18, and 24 months post-randomisation. This dosing regimen is in adherence to the approved schedule in the Decapeptyl SmPC for the indication of precocious puberty in the same age group, used in routine clinical care. In cases of documented tolerability issues, inadequate suppression of puberty, or product unavailability, alternative regimens may be implemented in accordance with expert panel recommendation and confirmation, as outlined in Appendix C with the following products:

- Decapeptyl® SR (long-acting formulation of Triptorelin) 11.25mg intramuscular injection (3 monthly preparation)
- Prostap 3 DCS (Leuprorelin Acetate) 11.25mg intramuscular injection (3 monthly preparation)
- Gonapeptyl (Triptorelin) 3.75mg intramuscular injection (1 monthly preparation)

5.2.4 Monitoring:

Following administration, participants will be monitored during their clinic visit for any immediate adverse reactions post-injection. The length of the monitoring period is determined by the principal or sub-investigator at the endocrine centre based on their clinical expertise.

Regular follow-up appointments to assess efficacy and safety, including monitoring hormone levels and physical development.

Routine blood tests, DEXA scans, and physical assessments (height, weight, BMI, blood pressure, body composition using Tanita scales if available, and puberty staging).

Psychosocial screening to identify any unmet needs and escalate these to appropriate services.

5.2.5 Fertility Preservation:

Discussion of fertility preservation options with referrals to fertility specialists if desired.

5.2.6 Comparator:

Delayed Start: Participants in the delayed start group will begin GnRHa treatment one year after randomisation. They will receive the same monitoring and assessments as the immediate start group.

5.3 IMP accountability

The Clinical Trials Pharmacy teams at recruiting sites will maintain records of medication dispensing and dosing.

Participants will be monitored for adherence to the injection schedule.

5.4 IMP Storage

GnRHa injections will be stored according to the SmPC. The clinical trial pharmacy team will ensure proper storage and handling of the medication as delegated by the PI.

5.5 Returns & Destruction

A record of study drug returns is not required as the intervention is administered in clinic as a single dose at each visit. IMP components should be disposed of in adherence to the Trust's pharmaceutical waste management procedures.

Any medicinal product not administered immediately following reconstitution for injection should be disposed of in accordance with local procedures and documented on the accountability log as not administered.

In the event the IMP is dispensed and not administered prior to re-constitution of the component parts, this should be documented on the master accountability log and the IMP may be re-dispensed.

5.6 Discontinuing allocated interventions

Participants may discontinue GnRHa treatment at any time without any detrimental impact on their care. Reasons for discontinuation will be documented, and participants will remain in follow-up according to their randomised arm's schedule of events until the end of the study .

Health care team-initiated discontinuation criteria include:

- Occurrence of any condition that, in the opinion of the Investigator, significantly jeopardizes the wellbeing and safety of the patient, including serious or intolerable AE that prevents the subject from continuing with study participation

The electronic version of this document is the latest version. It is responsibility of the individual to ensure that any paper material is the current version. Printed material is uncontrolled documentation.

- Change in compliance with any inclusion or exclusion criterion that is clinically relevant and affects subject safety, as determined by the Investigator.
- Use of prohibited concomitant medications
- QTc > 470ms
- Pregnancy

When the health care team are considering discontinuation, they will discuss the reasons for this with the participant and their parents/ legal guardians, taking account of their preferences and possible alternative treatment regimes.

5.7 Concomitant medications permitted or prohibited during the trial

5.7.1 Permitted Medications

Participants may continue to take other medications as prescribed by their healthcare providers.

Any changes in medication will be documented and monitored for potential interactions with GnRHa.

Medications known to affect pituitary gland function or increase prolactin levels (e.g. risperidone) should not be prescribed concomitantly. This includes certain antipsychotics (e.g. risperidone) and metoclopramide. Where such medications are clinically indicated, the potential risks but should be carefully considered. If no suitable alternatives are available, additional monitoring is required.

5.7.2 Prohibited medications

Gender affirming hormones are prohibited for participants in this study.

Prolonged use of medicinal products associated with clinically relevant bone mineral density loss, such as systemic glucocorticoids (for >14 days) and traditional anticonvulsants (e.g. phenytoin, phenobarbital, carbamazepine, valproic acid).

Use of puberty blockers outside this clinical trial.

Any other investigational medicinal products (IMPs).

Drugs known known to prolong QT interval, specifically: IA antiarrhythmics (e.g. quinidine, disopyramide), class III antiarrhythmics (e.g. amiodarone, sotalol, dofetilide, ibutilide), and methadone.

5.7.3 Non-prohibited Concomitant Potentially QT-Prolonging Drug Risk Management Algorithm

Including but not limited to – moxifloxacin, selective serotonin reuptake inhibitors (SSRIs), Tricyclic antidepressants, and antipsychotic agents.

Objective:

The electronic version of this document is the latest version. It is responsibility of the individual to ensure that any paper material is the current version. Printed material is uncontrolled documentation.

To minimise the risk of QT interval prolongation and Torsade de Pointes in participants receiving GnRHa therapy.

Step 1: Baseline Risk Assessment

Review participant's medication list for known non prohibited QT-prolonging drugs (e.g., SSRIs, antipsychotics).

Assess personal/family history of:

- Congenital long QT syndrome (LQTS)
- Unexplained syncope or sudden cardiac death

Step 2: Risk Stratification

Low Risk: No QT-prolonging drugs, no cardiac history.

Moderate Risk: Single QT-prolonging drug.

High Risk: ≥ 2 QT-prolonging drugs, congenital LQTS, Family history

Step 3: Management Actions

Low Risk:

- Proceed with only baseline ECG unless symptoms develop.

Moderate Risk:

- ECG at baseline and after dose initiation.
- Avoid adding further QT-prolonging drugs.

High Risk:

- Obtain cardiology review before enrolment.
- QTcF ≥ 470 ms or cardiologist advises against, exclude participant.
- ECG confirmation and after every administration.

Step 4: Ongoing Monitoring

Repeat ECG only if:

- QT-prolonging drug added
- Symptoms (syncope, palpitations) occur
- Investigator deems clinically indicated

Step 5: Discontinuation Criteria

- Confirmed QTcF >470 ms OR cardiologist opinion of clinically significant risk.

The electronic version of this document is the latest version. It is responsibility of the individual to ensure that any paper material is the current version. Printed material is uncontrolled documentation.

6 Assignment of Interventions

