3.2.1.3 Clinical Exclusion Criteria

1. Physical conditions where puberty will not commence or advance in a patient. This may include gonadal failure (e.g. due to genetic disorders such as Turner syndrome) or central hypogonadotropic hypogonadism.
2. Unstable physical health. The purpose of this criterion is to ensure that the CYP is not undergoing concurrent high-intensity physical interventions which might affect their response to GnRHa or their ability to adhere to the trial protocol. These include but are not limited to:
 - a. Very low or very high BMI (or rapid changes in BMI), particularly if there is a concerning trajectory or associated nutritional or metabolic concerns. This could include eating disorders or body dysmorphic disorder.

The electronic version of this document is the latest version. It is responsibility of the individual to ensure that any paper material is the current version. Printed material is uncontrolled documentation.

- b. Any poorly controlled medical disorder, such as uncontrolled epilepsy, inflammatory bowel disease, cystic fibrosis. This includes any other condition where participation may pose a risk to the individual's health or compromise study integrity.
- c. Concerns about bone health or significant risk of fractures (this may also include a low baseline bone density).
- d. QTc interval above 470 milliseconds at screening, or concomitant high-risk QT-prolonging drugs that cannot be ceased

3. Hypersensitivity to gonadotropin releasing hormone (GnRH), its analogues, or to any of its excipients
4. Known congenital long QT syndrome
5. Unstable mental health that may impair ability to provide informed assent/consent or lead to risk of serious harm to self or others. Many CYP with gender incongruence experience anxiety and/or depression which they relate to gender dysphoria or distress. It is not the intention to exclude those with mild to moderate levels of mental health symptoms. However, severe or unstable symptoms may affect the ability to engage in all aspects of the clinical protocol. Examples would include (but are not limited to):
 - a. Severe or profound depression with significant effects on the ability to accurately evaluate choices and future outcomes;
 - b. Severe body dysmorphic disorder that is confounded with secondary sexual characteristics or physique not conforming to the desired gender;
 - c. Active psychotic symptoms;

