4.14.2 Electrocardiogram (ECG)

A 12-lead ECG will be collected at screening for systemic cardiac monitoring. ECGs will be collected at follow up visits where indicated clinically.

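### The QT safety rules contradict each other on congenital long QT and on post-dose ECGs, and differ in detail on the 470 ms limits

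*Protocol*

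**What the plan says.** **Congenital long QT.** Protocol 3.2.1.3 lists "Known congenital long QT syndrome" as a clinical exclusion with no qualification, and the synopsis repeats it. Step 2 of 5.7.3 reads "High Risk: ≥ 2 QT-prolonging drugs, congenital LQTS, Family history". Step 3 sends that group to cardiology review before enrolment and then applies "QTcF ≥ 470 ms or cardiologist advises against, exclude participant".

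**ECG timing.** For Moderate Risk, meaning a single QT-prolonging drug, Step 3 requires "ECG at baseline and after dose initiation". For High Risk it requires an ECG after every administration. Step 4 then says "Repeat ECG only if" one of three things happens: a QT-prolonging drug is added, symptoms such as syncope or palpitations occur, or the investigator judges it indicated. Section 4.14.2 provides an ECG at screening and adds that "ECGs will be collected at follow up visits where indicated clinically". Tables 2, 4 and 5 mark ECG in the screening column only, with no footnote.

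**Limits.** Section 3.2.1.3 excludes a "QTc interval above 470 milliseconds at screening" and names no correction formula. Section 5.6 stops treatment at a QTc above 470 ms, again with no formula and no need for confirmation. Step 5 of 5.7.3 stops treatment at a confirmed QTcF above 470 ms, or on a cardiologist's opinion of clinically significant risk.

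**The concern.** These rules decide who may enter, who is monitored and who stops treatment. The protocol itself treats QT as a risk: 8.3 lists QT prolongation among rare adult effects, and the stated aim of 5.7.3 is to minimise QT prolongation and Torsade de Pointes. If the sections disagree, two sites can treat identical participants differently while each points to protocol text in support. A site working from the schedule of events may also omit ECGs that Step 3 requires. The discontinuation limit would then have no routine measurement behind it for the participants whom the algorithm singles out as at higher risk.

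**Working it through.** There is no planned figure to reproduce. The check sets the passages side by side and adds simple counts.

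**1. Congenital long QT.** Take a known case with QTcF below 470 ms and no cardiologist objection.
- 3.2.1.3: excluded.
- 5.7.3 Steps 2 and 3: High Risk, cardiology review, and neither ground for exclusion is met.

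The Step 2 entry cannot mean family history alone, because family history is listed separately on the same line. Nor can it be confined to cases found after entry, because the action is placed before enrolment.

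**2. Post-dose ECGs.** Section 5.2.3 gives injections at 0, 6, 12, 18 and 24 months. Table 5 starts the delayed arm at Month 12, so its injections fall at 12, 18 and 24 months. On the six-monthly preparation:

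| Group | Step 3, immediate arm | Step 3, delayed arm | Marked in Tables 4 and 5 |
|---|---|---|---|
| Moderate Risk | 1 | 1 | 0 |
| High Risk | 5 | 3 | 0 |

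Neither risk group nor injection is a trigger in Step 4. The missing marks are not simply a table convention, since other conditional procedures carry footnotes, such as the extra safety review on switching preparation. The minimum content of that review (4.16) does not include an ECG either.

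In the delayed arm the one scheduled ECG also comes long before treatment. Screening is up to 12 weeks before Day 0, and the Month 12 window is 4 weeks either side. Taking 12 months as 52 weeks, the gap runs from 52 − 4 = 48 weeks to 52 + 4 + 12 = 68 weeks.

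**3. The 470 ms limits.** Each rule is applied to the same numerical reading:

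| Rule | 469 ms | 470 ms | 471 ms |
|---|---|---|---|
| 3.2.1.3, exclude, QTc > 470 | no | no | yes |
| 5.7.3 Step 3, exclude if High Risk, QTcF ≥ 470 | no | yes | yes |
| 5.6, stop, QTc > 470 | no | no | yes |
| 5.7.3 Step 5, stop, QTcF > 470 (if confirmed) | no | no | yes |

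The inequality matters at one integer value, and only for High Risk participants. The correction formula can matter more. Suppose, as an assumption the protocol does not state, that the unnamed QTc were read as Bazett (QT/RR^(1/2)), while QTcF is Fridericia (QT/RR^(1/3)). Then QTcB = QTcF × RR^(−1/6), with RR = 60/heart rate. A QTcF of 470 ms corresponds to:
- 60/min: 470 × 1.0000 = 470 ms
- 75/min: 470 × 1.0379 = 488 ms
- 90/min: 470 × 1.0699 = 503 ms
- 100/min: 470 × 1.0889 = 512 ms

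If both are read as Fridericia, the gap is zero. Separately, one unconfirmed reading above 470 ms meets 5.6 but not Step 5.

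**The case against.** The best defence is that the passages can be applied together. Step 3 never says that cardiology review overrides an exclusion criterion, and 4.10.2 requires all eligibility checks to be complete before randomisation. A site applying both sections would therefore exclude a known long QT case. Step 4 is headed as ongoing monitoring and could mean repeats beyond those Step 3 assigns. The schedules may show only assessments common to everyone, and 4.14.2 leaves room for others. A slightly stricter limit for a High Risk subgroup does not contradict a general one, and QTcF is a form of QTc.

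Part of this stands. It disposes of any inference that known long QT cases will be enrolled, and it reduces the threshold difference to a minor point. It does not remove the two main conflicts. If the exclusion always governs, the long QT entry in Step 2 has no function and its conditional exclusion misleads. The restrictive wording of Step 4 rules out the routine Step 3 ECGs unless the reader supplies a qualification that is not written, and no schedule corrects that reading.

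A reader might go further and infer that the discontinuation rule cannot operate. That is too strong: ECGs prompted by symptoms, an added drug or the investigator, and any done under Step 3, could still invoke it. Nor do the documents show that QT-relevant drugs are common here. Section 5.7.3 names SSRIs and antipsychotics, and 3.2.1.3 says many of these young people have anxiety or depression, but no prevalence of use is given. Section 5.7.1 advises against certain antipsychotics.

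**Conclusion.** Two contradictions hold in the current text: unconditional against conditional exclusion for known congenital long QT, and required post-dose ECGs in Step 3 against the restriction in Step 4 and the screening-only schedules. On the six-monthly preparation the second amounts to one ECG (Moderate Risk) or three to five (High Risk) that a site following the schedule may omit. For those participants the discontinuation limit lacks a routine measurement, though triggered ECGs remain possible. The third element is minor on the inequality, at exactly 470 ms only, but the unnamed formula and the differing confirmation requirement need settling. The Bazett figures rest on an assumption and show only why the formula should be named. The number of participants affected cannot be derived from the protocol. The matter should be corrected because it bears on participant safety and is cheap to resolve.

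**What to change.** The sponsor's clinicians should reconcile 3.2.1.3 (and the synopsis), 4.14.2, 5.6, Steps 2 to 5 of 5.7.3 and the schedules of events. The passages should then state:
- one position on known congenital long QT;
- one correction formula, and one statement of whether a reading must be confirmed;
- consistent 470 ms wording, with any intended subgroup difference stated as such;
- one statement of ECG timing by risk group, with Step 4 worded to fit Step 3, and Tables 2, 4 and 5 showing whatever is decided, including for the delayed arm's first injection.

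This review takes no view on which limit, exclusion or ECG timing is right. The reconciliation itself costs a wording amendment and a schedule row or footnote. Whether it changes the number of ECGs performed depends on what the clinicians decide.
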